Upon completion and unblinding of the double-blind studies EN3835-302/303 (see [Figure 1](#)), subjects who received placebo during the double-blind studies will be discontinued, and subjects who received active CCH will be classified into one of three Categories:

- Category I: 1-Level Composite Responders
- Category II: 2-Level Composite Responders
- Category III: Non-Composite Responders

Composite response will be assessed using both the subject PR-PCSS (Patient Reported Photonumeric Cellulite Severity Scale) responder classification and investigator CR-PCSS (Clinician-Reported Photonumeric Cellulite Severity Scale) responder classification, where same level of improvement is observed by both the scales in the same buttock (eg, for 2 level composite improvement – the improvement in response of at least 2-level should be observed in both PR-PCSS and CR-PCSS for the same buttock).

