3.1.1. Category I

- Subjects should have not received any collagenase treatments since the completion of the double-blind study.
- Subjects in which the maximum composite response was ONLY a 1-level composite improvement in cellulite severity at Day 71 as assessed by the PR-PCSS and CR-PCSS in either (or both) buttock(s) in the double-blind study. In cases where improvement was in both buttocks, the composite improvement of 1-level must have occurred in the same buttock (ie, the PR-PCSS and CR-PCSS improvement observed in the same buttock).
- Subjects who showed a 2-level improvement in one scale but only a 1-level improvement in the other scale, provided the composite improvement of 1-level was within the same buttock.
- Only buttocks with a composite 1-level improvement or less will be retreated.

- These subjects will be observed for time to reduction of response (defined in section 4.4.1) and safety approximately every 6 months for 2 years and will be observed annually for up to 3 years (Day 1080) from Day 71 of the double-blind study.

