 - ⁱ Up to 4 hours before injection; approximately 15 and 30 minutes after injection. Pulse and blood pressure to be taken after subject has been sitting for 5 minutes. Vital signs must be stable before the subject is discharged. Refer to section 14.9 of Protocol Amendment 3.
 - ^j Do not conduct if Screening B visit date is within 12 months of obtaining an ECG during the double-blind study (EN3835-302/303).
 - ^k Serum pregnancy test on Screening visit and Day 71/EOS visit; urine pregnancy test on Day 1, Day 22, and Day 43 visits and Unscheduled Visit.
 - ^l Assessment made via photographs (if treatment visit, use photographs taken before marking dimples and injection sites).
 - ^m Subject assessments should be completed independently and prior to investigator assessments at each visit. Includes bot buttocks regardless of treatment, each buttock should be assessed independently.
 - ⁿ At least one of the Category I subject’s buttocks must have scores/ratings of at least 2 in both the CR-PCSS and PR-PCSS to be eligible to receive treatment. Category II subjects must have at least a 1-level composite response reduction compared to Day 71 of the EN3835-302/303 study AND no longer maintain a 2-level composite response compared to baseline in the EN3835-302/303 study on either or both buttocks.
 - ^o Local adverse events associated with the injection site, including acute (eg, erythema, bruising, pain, nodules/mass, ulceration, blistering, pruritus, swelling, and/or induration) and/or chronic (eg, skin thickening, fibrosclerosis, peau d’orange changes) cutaneous adverse events, will be recorded and evaluated for seriousness and severity.
- ECG=Electrocardiogram; EFP=Edematous fibrosclerotic panniculopathy; EOS=End of study; Tx=Treatment.

The Schedule of Events beyond Day 180 for subjects in Category I and II who are eligible and opted to receive retreatment, for the subjects in Category II who are not eligible for retreatment, and Category I and II subjects who are eligible but opted not to have retreatment is provided in [Table 3](#).

Table 3: Schedule of Events: Category I/II Subjects – Observation Assessments

	OBS Visit 2 Day 360 (±30 d) (M12)	OBS Visit 3 Day 540 (±30 d) (M18)	OBS Visit 4 Day 720 (±30 d) (M24)	OBS Visit 5 Day 1080/EOS/Early Termination (±30 d) (M36)	Durability Confirmation Visit^b
Procedures^a					
Verification of informed consent	X				
Inclusion/exclusion	X				
Digital photography	X	X	X	X	X

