2-level Responder	Improvement in the PR-PCSS or CR-PCSS ratings of at least 2 levels compared to the ratings at Day 1 of double-blind study.	Improvement in the PR-PCSS or CR-PCSS ratings of at least 2 levels compared to the ratings at Day 1 of the Treatment Session of this study.
1-level Responder	Improvement in the PR-PCSS or CR-PCSS ratings of at least 1 levels compared to the ratings at Day 1 of double-blind study.	Improvement in the PR-PCSS or CR-PCSS ratings of at least 1 levels compared to the ratings at Day 1 of the Treatment Session of this study.
2-level Composite Responder	Subject who is both 2-level PR-PCSS responder and a 2-level CR-PCSS responder.	
1-level Composite Responder	Subject who is both 1-level PR-PCSS responder and a 2-level CR-PCSS responder.	

Note: If the classification is missing for 1 or both components (ie, the PR-PCSS component or the CR-PCSS component), then the composite responder classification is missing for that visit.

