Open Label Retreated (OLR) Population	The OLR Population includes all subjects in TRR population who are retreated in the open label period of this study.	The analyses of cellulite assessments after retreatment ie, improvement of response during retreatment phase (Day 1 to Day 71+5 days of retreatment), study drug exposure during retreatment, Safety assessments after retreatment will be based on this population.
Open Label Not Retreated (OLNR) Population	The Open Label Not Retreated Population includes all subjects in TRR Population who are NOT retreated in the open label period of study.	All analyses for change from baseline in Day 1, or Day 71, and responder analysis based on this population will be performed
Time to Reduction of Response (TRR) Population After Retreatment	The TRR Population After Retreatment includes all subjects in OLR Population who have at least 1 level or 2-level improvement in both CR-PCSS and PR-PCSS ratings at Day 71/End of Treatment Session in the open label retreatment period. Reduction of response will be evaluated separately for subjects who have at least a 1-level and 2 level improvement in both CR-PCSS and PR-PCSS ratings during the open label treatment period in each treated buttock. The reduction of response after retreatment will be analyzed using this population.	The reduction of response in open label retreatment period compared to the score at Day 71 of retreatment period will be based on this population.

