Baseline for Reduction of response and Improvement in Cellulite Severity (CR-PCSS and PR-PCSS)	
Improvement in Cellulite Severity: The assessment performed at Day 1 during the retreatment phase will be used as baseline to evaluate improvement in cellulite severity at Day 71 in this study.
 
Reduction of Response Prior to Retreatment: The assessment performed at Day 71/EOS visit in the double-blind phase will be used as baseline to evaluate reduction of response for any visits prior to/on first dose date of retreatment in this study.
 
Reduction of Response After Retreatment: The assessment performed at Day 71/End of treatment Session in the retreatment phase will be used as baseline to evaluate reduction of response during the observation phase after retreatment.

Baseline for CR-PCSS, PR-PCSS and PR-CIS Score	
At 180 Day Evaluation: The Screening assessment done within 14 days of Day 71/EOS of double-blind period will be used as baseline for 180 Day Evaluation period.
 
Before Retreatment: The Screening assessment done within 14 days of Day 71/EOS of double-blind period will be used as baseline for open-label period for subjects in TRR population who are not retreated, and until the point prior to retreatment for the subjects who are retreated.
 
After Retreatment: The assessments at Screening B/unscheduled assessment or Day 1 of the retreatment phase prior to/on the first dose date of retreatment in this study will be used as baseline.

Baseline for S-GAIS and Subject Satisfaction with Cellulite Treatment	The pretreatment Day 1 digital images from the double-blind study (EN3835-302/303) will be used as baseline.
Change from Baseline	Change from baseline will be derived as, post-baseline visit/time point value – the baseline value.
Time to reduction of response prior to retreatment (duration in days)	Date of visit where reduction is detected first – Date of Day 71/EOS of double-blinded studies 302/303
Time to reduction of response after retreatment (duration in days)	Date of visit where reduction is detected first – Date of Day 71/End of Treatment Session of open-label retreatment phase
Time to Complete Loss of Response prior to retreatment (duration in days)	Date of visit where complete loss of response reduction is detected first – Date of Day 71 of double-blinded studies 302/303 OR Date of Day 71/End of Treatment Session of open-label retreatment phase

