7.6.4. Improvement of Response using PR-PCSS and CR-PCSS

The improvement of response in cellulite severity is assessed in the open-label study for the subjects who received retreatment. The cellulite severity assessment during retreatment phase will be used for this analysis. The proportion of subjects with improvement in response compared to cellulite assessments at Day 1 prior to retreatment (refer to section **Error! Reference source not found.**) will be summarized using frequency counts and percentages using OLR Population by subject category (ie, Category I and II, and Overall) and treatment area (ie, separately for left and right buttock) at Day 22, 43, and 71 following retreatment:

- Proportion of 2-level composite responders
- Proportion of 1-level composite responders
- Proportion of 1-level and 2-level CR-PCSS responders
- Proportion of 1-level and 2-level PR-PCSS responders

The above responder analysis will be repeated considering Day 1 of double blinded study as reference.

The listings of cellulite PR-PCSS and CR-PCSS severity ratings will be provided for subjects in OLR Population after Retreatment.

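### Table 13 requires a 2-level CR-PCSS response for a 1-level composite responder, so the 1-level composite proportion in section 7.6.4 is under-counted if coded as written

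*SAP*

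**What the plan says.** The last row of Table 13 (section 4.4.2) defines a 1-level composite responder as: "Subject who is both 1-level PR-PCSS responder and a 2-level CR-PCSS responder". One entry is given, with no separate wording for the period after retreatment. The row above it, for the 2-level composite responder, asks for a 2-level response on each scale. The single-scale rows of the table define a 1-level responder by an improvement of at least 1 level and a 2-level responder by at least 2.

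Elsewhere the SAP treats the two scales alike:

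- Section 3.1 describes composite response as one "where same level of improvement is observed by both the scales in the same buttock".
- Section 3.1.1 takes into Category I subjects whose best result was "ONLY a 1-level composite improvement in cellulite severity at Day 71 as assessed by the PR-PCSS and CR-PCSS". It also admits those with 2 levels on one scale and 1 on the other, without saying which scale must be the higher.
- Section 5 defines the TRR Population After Retreatment as subjects "in OLR Population who have at least 1 level or 2-level improvement in both CR-PCSS and PR-PCSS ratings at Day 71/End of Treatment Session".

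Section 7.6.4 lists "Proportion of 1-level composite responders" among its outputs for the OLR Population, by category and buttock, at Days 22, 43 and 71 of retreatment. It then repeats the analysis against Day 1 of the double-blind study. Where that section should point to the definition, it prints "Error! Reference source not found".

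**The concern.** A composite endpoint at a given level should need that level on both components. This row mixes levels, so the plainest 1-level composite response, one level on each scale, is classed as non-response. Nothing else in the SAP restates or corrects the row, and the broken reference in section 7.6.4 leads the programmer nowhere. Table 13 is therefore the only definition of the term available for programming.

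Two things are at stake. First, the reported proportion of 1-level composite responders after retreatment would be too low against both reference points. Second, the output would sit awkwardly beside the SAP's own population table. The TRR Population After Retreatment is drawn from the same OLR subjects at the same retreatment Day 71 visit, and for improvement at that visit Table 17 states: "The assessment performed at Day 1 during the retreatment phase will be used as baseline to evaluate improvement in cellulite severity at Day 71". On that baseline, a buttock with 1 level on both scales brings the subject into the population but counts as a non-response in section 7.6.4.

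A neighbouring slip belongs in the same correction. The 1-level Improvement row of Table 13 says at least 1 level but glosses this as a change of -2 or -3, the same as the 2-level row. Both glosses omit -4, which a 0 to 4 scale allows. The reduction rows of the same table do list changes up to 4. This slip does not feed the responder proportions in section 7.6.4, because the single-scale responder rows are worded correctly.

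**Working it through.** The SAP states no rate, power or sample size for this endpoint, so there is no figure to reproduce. The check is a count of outcome patterns.

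**Inputs**
- Both scales run from 0 to 4 (Tables 6 and 7), so improvement is at most 4 levels.
- A 1-level responder has an improvement of at least 1, and a 2-level responder at least 2 (Table 13).
- Rule as written (Table 13): PR ≥ 1 and CR ≥ 2.
- Same-level rule (section 3.1): PR ≥ 1 and CR ≥ 1.

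PR and CR are the levels of improvement on PR-PCSS and CR-PCSS in one buttock.

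**All patterns**
- Same-level rule: 4 × 4 = 16 pairs.
- Rule as written: 4 × 3 = 12 pairs.
- Lost: 16 − 12 = 4, namely (PR, CR) = (1,1), (2,1), (3,1) and (4,1).
- Gained: none, since every pair that meets the written rule also meets the same-level rule.

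A buttock with CR = 1 and no PR-PCSS improvement fails both rules and is not part of the loss.

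**Separation from the 2-level endpoint**
- The 2-level composite (PR ≥ 2 and CR ≥ 2) covers 3 × 3 = 9 pairs.
- Under the same-level rule, 16 − 9 = 7 pairs are 1-level but not 2-level composite responses.
- As written, 12 − 9 = 3 remain: (1,2), (1,3) and (1,4).

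The 1-level proportion is thus pulled towards the 2-level one.

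**By starting score**, taking the same Day 1 score s on both scales. Improvement is then limited to s, which gives s × s pairs under the same-level rule and s × (s − 1) as written.

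| Day 1 score on both scales | Same-level rule | As written | Lost |
|---|---|---|---|
| 2 | 4 | 2 | 2 |
| 3 | 9 | 6 | 3 |
| 4 | 16 | 12 | 4 |

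A score of 2 is relevant because Table 2, footnote n, says that at least one buttock of a Category I subject "must have scores/ratings of at least 2 in both the CR-PCSS and PR-PCSS to be eligible to receive treatment". For a buttock starting retreatment at 2 on both scales, only a fall to CR-PCSS 0, together with some PR-PCSS improvement, would count.

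These are counts of possible outcomes. They are not proportions of subjects, and no distribution over the patterns is assumed.

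**The case against.** The strongest reply is that this is a typing slip that any reader would see through. The row above is symmetric, sections 3.1, 3.1.1 and 5 all point to the same level on both scales, and Table 18 lists no change to the responder definition. It very probably is a slip. But it stands in the operative definition, and a programmer must either code it as written or depart from the SAP without authority. The intention is clear, but the rule on the page still needs correcting.

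Other points limit the claim:

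- **Descriptive endpoint.** Section 7.6.4 gives counts and percentages only. This stands and keeps the consequence modest.
- **Unseen table shells.** Section 11 places layouts and footnotes in SAP Module 2, which was not available. A correction there is possible, so the effect is conditional on literal coding. The shells are no evidence that a correction exists.
- **Pattern counts are not rates.** This stands. The footnote on scores of at least 2 applies at Screening B and to at least one buttock, so it does not fix the Day 1 score of every buttock summarised. It also says nothing about scores at double-blind Day 1.
- **The mismatch with the TRR population.** Section 5 names no reference visit for improvement. One row of Table 17 gives retreatment Day 1, but another allows Screening B, an unscheduled assessment or Day 1 as the after-retreatment baseline for the same scales. The mismatch follows on the first of these rows. The error in the definition does not depend on it.

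**Conclusion.** The concern holds. Table 13 states a rule that contradicts the SAP's own definition of composite response. If coded as written, it removes every buttock with exactly 1 level of CR-PCSS improvement and at least 1 level of PR-PCSS improvement from the 1-level composite responders. That is 4 of 16 qualifying patterns, with none added, so the error is always downward. Its size in subjects cannot be given, because the SAP states no response rates or joint distribution of the two scales.

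The effect is confined to the descriptive 1-level composite proportions in section 7.6.4, against both retreatment Day 1 and double-blind Day 1. The Category I to III columns, the TRR populations, the 2-level composite proportion and the single-scale proportions rest on other wording and do not change. The conclusion assumes only that outputs are programmed from Table 13 and that no document outside this SAP overrides it.

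**What to change.** In Table 13:

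- Define the 1-level composite responder as a subject who is a 1-level responder on PR-PCSS and a 1-level responder on CR-PCSS in the same buttock.
- Add the same-buttock condition to the 2-level composite row as well, so that the two adjacent rows match each other and section 3.1.
- Gloss 1-level Improvement as a change of -1, -2, -3 or -4, and 2-level Improvement as -2, -3 or -4, in both columns.

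In section 7.6.4, repair the cross-reference so that it points to section 4.4.2, Table 13. Check the shells in SAP Module 2 for the same wording.

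The cost is a few lines of SAP text and at most one line of code. No new data are needed and no other endpoint changes.

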4.4.3. Patient Reported Cellulite Impact Scale Total Score

A PR-CIS total score and an abbreviated PR-CIS score (excluding question 5) will be derived from 6 individual questions (refer to section 3.8.2.4) for a region, ie, two buttocks during evaluation.

The PR-CIS total score will be derived by adding the ratings of the 6 items on the scale. Item #1 on the PR-CIS asking – “how happy the subject is about their appearance of cellulite” will be reversed by subtracting the subject’s reported assessment from 10 (ie, for purposes of the composite, scoring for the “happy” question is reversed (reflected) to make it directionally consistent with the other questions). In this manner, a higher number on 6 of the PR-CIS questions will reflect a more negative impact.

The PR-CIS total score will range from 0 to 60 with higher numbers reflecting more negative impact from the cellulite. If scores on two or less of the 6 items are missing, then the PR-CIS total score will be calibrated to 6 and computed as:

- Total PR-CIS Score = (Sum of the Scores ÷ Number of questions answered) x 6

If scores on three or more of the 6 items are missing, then the PR-CIS total score will be set to missing.

Similarly, the PR-CIS abbreviated total score will be derived by adding the sum of the five items (Items #1-4 and Item #6) on the scale (note that for the abbreviated total score Item #1 score should be replaced by the value generated by subtracting the item score from 10). The PR-CIS abbreviated total score will range from 0 to 50 with higher numbers reflecting more negative impact from the cellulite. If scores on two or less of the 5 items are missing, the PR-CIS abbreviated total score will be computed as:

- Abbreviated total PR-CIS Score = (Sum of the Scores ÷ Number of questions answered) x 5

If scores on three or more of the five items are missing, then the PR-CIS abbreviated total score will be set to missing.

4.4.3.1. Change from Baseline of PR-CIS Item or Total or Abbreviated Total Scores

The change from Day 1 of the double-blind study for PR-CIS is defined as PR-CIS score (item or total or abbreviated total) at respective visit minus PR-CIS score at Day 1 of the double-blind study.

The change from Day 71/EOS of the double-blind study for PR-CIS is defined as PR-CIS score (item or total or abbreviated total) at respective visit minus PR-CIS score at Day 71/EOS of the double-blind study.

The change from Day 1 of retreatment period for PR-CIS score (item or total or abbreviated total) will be the visit score minus the Day 1 of retreatment period score.

For Item #1, a more positive change in score indicates a greater improvement of impact of the cellulite on subject's happiness while for other items a more negative change in score indicates a greater reduction of impact of the cellulite on subject's life.

4.4.3.2. Responders based on Baseline PR-CIS Item or Total or Abbreviated Total Scores

A PR-CIS (item or total or abbreviated total) responder with respect to Day 1 of double-blind study is defined as a subject with a reduction in the PR-CIS score (item or total or abbreviated total) of at least 2 from Day 1 of double blind study at an evaluation time point.

A PR-CIS (item or total or abbreviated total) responder with respect to Day 71/EOS of double-blind study is defined as a subject with a reduction in the PR-CIS score (item or total) of at least 2 from Day 71/EOS of double blind study at an evaluation time point.

A PR-CIS (item or total or abbreviated total) responder with respect to Day 1 of retreatment period of this study is defined as a subject with a reduction in the PR-CIS score (item or total) of at least 2 from Day 1 of retreatment period of this study at an evaluation time point.

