7.6.5. Changes in the PR-CIS Scores from Baseline

The PR-CIS scores (Each item, total, and abbreviated) will be analyzed separately at Day 180 using Day-180 Observational Population and Prior to Day 180 Population, for the data before retreatment using TRR Population Before Retreatment, and OLNLR Population and data for after retreatment using OLR Population.

At Day 180 Evaluation

The observed and/or change from baseline in PR-CIS item scores, total, and abbreviated scores (refer to section 4.4.3) of the subjects in 180 – Day Observational Population will be summarized descriptively by treatment arm (ie, CCH 1.68 mg, Placebo, and Overall) at overall treatment area

(ie, two buttocks). The Screening assessments done at Day 71/EOS visit in the double-blind studies will be used as baseline.

Also, the observed and/or change from Day 1 of double blind studies (302/303) in PR-CIS item scores, total, and abbreviated scores (refer to section 4.4.3) of the subjects up to Day 180 in 180–Day Observational Population and Prior to Day 180 Population will be summarized descriptively by treatment arm (ie, CCH 1.68 mg, Placebo, and Overall) at overall treatment area (ie, two buttocks).

Before Retreatment

The observed and/or change from baseline and change from Day 1 of double-blinded studies in PR-CIS item scores, total, and abbreviated scores (refer to section 4.4.3) of the subjects who did not receive retreatment and the data until the point prior to retreatment for the subjects who are retreated will be summarized descriptively using TRR Population Before Retreatment and OLNLR Population by subject category (ie, Category I and II, and Overall) at overall treatment area (ie, two buttocks) and assessment visits: Day 180, Month 12, 18, 24, and 36.

The Screening assessments done at Day 71/EOS visit in the double-blind studies will be used as baseline.

Also, the observed and/or change from Day 1 of double blind studies (302/303) in PR-CIS item scores, total, and abbreviated scores (refer to section 4.4.3) of the subjects who did not receive retreatment and the data until the point prior to retreatment for the subjects in TRR Population and OLNLR Population will be summarized descriptively by subject category (ie, Category I and II, and Overall) at overall treatment area (ie, two buttocks).

After Retreatment

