7.6.7. Responder Analysis based on Baseline PR-CIS Scores

The PR-CIS responders (Each item, Total, and Abbreviated) will be analyzed separately at Day 180 using Day-180 Observational Population, for the data before retreatment using TRR Population Before Retreatment, and data after retreatment using OLR Population.

At Day 180 Evaluation

The proportion of PR-CIS responders based on item scores, total, and abbreviated scores (refer to section 4.4.3) of the subjects in 180 – Day Observational Population will be summarized using frequency counts and percentages by treatment arm (ie, CCH 1.68 mg, Placebo, and Overall) at overall treatment area (ie, two buttocks).

Before Retreatment

The proportion of PR-CIS responders based on item scores, total, and abbreviated scores (refer to section 4.4.3) of the subjects who did not receive retreatment and the data until the point prior to retreatment for the subjects who are retreated will be summarized using frequency counts and percentages for subjects in TRR Population Before Retreatment by subject category (ie, Category I and II, and Overall) at overall treatment area (ie, two buttocks) and assessment visits: Day 180, Month 12, 18, 24, and 36.

After Retreatment

The proportion of PR-CIS responders based on item scores, total and abbreviated scores (ie, based on scores as compared to baseline - refer to section 4.4.3) at Day 71 of the retreatment session and other observational visits of the subjects who are retreated in the open label study will be summarized using frequency counts and percentages for subjects in OLR Population by subject category (ie, Category I and II, and Overall) at overall treatment area (ie, two buttocks).

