7.6.8. Responder Analysis based on Day 71 Open-label Period PR-CIS Scores

The proportion of PR-CIS responders based on item scores, total and abbreviated scores (ie, based on scores as compared to Day 71 of open-label period - refer to section 4.4.3) at observational visits after retreatment will be summarized using frequency counts and percentages for subjects in OLR Population by subject category (ie, Category I and II, and Overall) at overall treatment area (ie, two buttocks).

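### The PR-CIS item responder rule runs backwards for Item 1: as written, becoming less happy counts as a response and becoming happier does not

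*SAP*

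**What the plan says.** The PR-CIS has six items, each rated from 0 (not at all) to 10 (extremely) (SAP section 3.8.2.4, Table 9). Item 1 asks about happiness with the appearance of the cellulite. The other five ask about bother, self-consciousness, embarrassment, looking older, and looking overweight or out of shape.

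- **Totals (4.4.3).** Item 1 is reversed for the composite score so that it points the same way as the other items. Likewise, "for the abbreviated total score Item #1 score should be replaced by the value generated by subtracting the item score from 10". With that reversal, "The PR-CIS total score will range from 0 to 60", and higher is worse.
- **Item-level change (4.4.3.1).** Item 1 keeps its own direction: "a more positive change in score indicates a greater improvement of impact of the cellulite" on happiness. For the other items a negative change is the favourable one.
- **Responders (4.4.3.2).** Against double-blind Day 1, a responder is "defined as a subject with a reduction in the PR-CIS score (item or total or abbreviated total) of at least 2 from Day 1". The definitions against double-blind Day 71/EOS and Day 1 of retreatment use the same 2-point reduction. None of the three treats Item 1 separately.
- **Outputs (7.6.7 and 7.6.8).** "The PR-CIS responders (Each item, Total, and Abbreviated) will be analyzed separately at Day 180", and then before and after retreatment. The Day 180 proportions are "summarized using frequency counts and percentages by treatment arm (ie, CCH 1.68 mg, Placebo, and Overall) at overall treatment area". Section 7.6.8 adds responders "based on scores as compared to Day 71 of open-label period - refer to section 4.4.3". Neither section adjusts the direction for Item 1.

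**The concern.** Sections 4.4.3.1 and 4.4.3.2 cannot both be right for Item 1. If a positive change is improvement, a responder rule that requires a reduction selects the subjects who got worse.

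The Item 1 responder percentage would then report deterioration as response in every PR-CIS responder table, next to seven rows that point the right way. The Day 180 table matters most because it sets CCH beside placebo. For that period section 7.6.5 states: "The Screening assessments done at Day 71/EOS visit in the double-blind studies will be used as baseline", and Table 17 agrees. On that baseline, a subject whose happiness falls by 2 or more after Day 71 would appear as an Item 1 responder. A reader would take a higher percentage in that row as better persistence of effect when it means the opposite.

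**Working it through.** **Inputs.** Item scale 0 to 10 and Item 1 wording: 3.8.2.4 and Table 9. Reversal (10 minus score) inside the totals: 4.4.3. Direction of Item 1 change: 4.4.3.1. Response rule, visit minus reference ≤ −2: 4.4.3.2.

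**Step 1: reproduce the plan's own ranges.** With Item 1 reversed inside the totals:
- Total: minimum (10 − 10) + 5 × 0 = 0; maximum (10 − 0) + 5 × 10 = 60.
- Abbreviated total (without Item 5): minimum (10 − 10) + 4 × 0 = 0; maximum (10 − 0) + 4 × 10 = 50.

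Both match 4.4.3, so the totals are oriented correctly and a reduction on them is an improvement.

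**Step 2: apply the rule to raw Item 1.** There are 11 × 11 = 121 possible pairs of reference and visit scores.
- Falls of 2 or more: the sum over d = 2 to 10 of (11 − d) = 9 + 8 + … + 1 = 45.
- Rises of 2 or more: 45, by symmetry.
- Within 1 point either way: 121 − 90 = 31.

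| Change in happiness | Pairs | Responders as written | Responders with Item 1 reversed |
|---|---|---|---|
| Rise of 2 or more (better) | 45 | 0 | 45 |
| Fall of 2 or more (worse) | 45 | 45 | 0 |
| Within 1 point | 31 | 0 | 0 |

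Every pair that differs by 2 or more is classified the wrong way round. This counts possible pairs; it is not an expected rate among subjects.

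**Step 3: one subject who improves by 3 on every item.**

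| Score | Reference | Visit | Change | Responder as written |
|---|---|---|---|---|
| Item 1 (raw) | 3 | 6 | +3 | No |
| Items 2 to 6 (each) | 7 | 4 | −3 | Yes |
| Total | (10 − 3) + 5 × 7 = 42 | (10 − 6) + 5 × 4 = 24 | −18 | Yes |
| Abbreviated total | (10 − 3) + 4 × 7 = 35 | (10 − 6) + 4 × 4 = 20 | −15 | Yes |

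She responds on seven of the eight rows and fails only on Item 1. The mirror subject, worse by 3 on every item, is a responder on Item 1 and on nothing else.

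**The case against.** The best counter-argument is a sentence in 4.4.3, directly after the reversal, saying that higher numbers on six of the questions then mean a more negative impact. Sections 7.6.7 and 7.6.8 refer back to 4.4.3, so a programmer might carry the reversed Item 1 into the item-level analysis, and the reduction rule would then run correctly. This does not rescue the text. The sentence describes scoring for the composite. If Item 1 were reversed throughout, the statement in 4.4.3.1 that a positive change is improvement would itself be wrong. On either reading the two sections conflict.

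The table layouts and footnotes are in SAP Module 2, which is not at hand, so a correction there cannot be excluded. That is a fair limit on predicting the final output, but it does not make the definition in 4.4.3.2 correct.

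The reach is also small. One descriptive row in eight is affected, and the Item 1 change-from-baseline summaries are correctly oriented, so an inverted responder row might be noticed beside them. All of this stands, and it bears on how serious the error is.

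**Conclusion.** The rule is wrong as written for Item 1. Applied to the raw item, it counts all 45 possible falls of 2 or more as response and none of the 45 possible rises. It affects one of eight PR-CIS responder rows (six items and two totals), at Day 180, before and after retreatment, and in the comparison with open-label Day 71.

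The conclusion assumes that the item-level score is the unreversed one, as 4.4.3.1 implies, and that the programming follows the SAP text. Items 2 to 6, the total and the abbreviated total are scored in the right direction. PR-CIS is in neither the primary nor the secondary objective, and no test or sample size depends on it. The correction should be made because a planned output would otherwise state the opposite of what happened, but it does not touch the study's main conclusions.

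**What to change.** In all three definitions in 4.4.3.2, state that Item 1 response is an increase of at least 2 in the raw score. Equivalently, apply the 2-point reduction to 10 minus the score, the reversal 4.4.3 already uses. Apply the same direction to the comparison with open-label Day 71 in 7.6.8. Say in 4.4.3 whether the reversal applies to the totals only, so that its sentence on the six questions no longer invites a second reading.

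The cost is one clause and one line of programming, with no new data. With the correction, all 45 rises of 2 or more count as response and none of the 45 falls does. Section 6.4 plans cellulite analyses at the Day 180 cutoff for the BLA submission, so any Item 1 responder row already produced should be checked against this rule and re-issued if it is inverted.
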